Microbiome study (26) suggested that patients with Th2-low asthma, the same group that responded in the AZISAST study, have a higher microbial burden than patients with the Th2-high phenotype. The AMAZES trial, in contrast, did not distinguish a difference in Th2-high versus Th2-low asthma in the efficacy of azithromycin on exacerbations. Differences in bacterial biomass or composition, all of which may reflect a dysbiotic microbiome, may be one key factor: azithromycin may work in these patients. None of the above-cited studies examined the microbiome, and so a key link to understand how macrolides might benefit patients with poorly-controlled asthma is missing. Neutrophilic asthma, one key Th2-low subtype, is associated with increased bacterial load and pathogens (identified by culture) such as *Hemophilus*, *Pseudomonas*, and *Moraxella* (48). Identifying the correct patient group may be the key to resolving the conflict of whether azithromycin is useful in asthma.

Why would a new study succeed where past, non-selective studies have failed? We hypothesize that in the right asthma phenotype – neutrophil dominant, Th2-low – modifying the dysbiotic microbiome in turn improves clinical control. Our trial will focus on the relation of asthma control to changes in the microbiome induced by azithromycin and understanding the influence of Th2-based phenotypes on this response. By careful examination of the dysbiotic microbiome, careful focus on Th2-low asthmatic patients, and focusing on patients with poor control in which the potential signal is substantial, we will answer the question definitively.

Purpose

The purpose of this protocol is to perform a short-term pilot study so as to acquire data critical to the proper design of a full-scale RCT. The primary objectives of the pilot study are to:

- a) Estimate variability of microbiome composition and diversity over time in control and asthmatic subjects to provide a baseline for the future RCT
- b) Estimate the response of the airway microbiome to azithromycin over time, so that we can generate appropriate power calculations and sample size estimates for the future RCT
- c) Refine our microbial informatics pipeline for the future RCT
- d) Refine our sputum gene expression and cytokine array testing
- e) Test the feasibility of our intervention in a small cohort of subjects with poorly-controlled asthma

Study Design

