This pilot protocol examines the change in the airway microbiome after azithromycin over an 8 week period. 40 subjects with poorly controlled asthma and 10 control subjects with no known lung disease will undergo clinical data collection including ACT score, lung function, exhaled nitric oxide (FeNO), methacholine challenge, and induced sputum and blood collection. Participants with asthma then are randomized 1:1 to receive azithromycin, 250 mg, or placebo, daily for 8 weeks. Clinical parameters including ACT, oral wash, adherence, side-effect profile, spirometry, and biological specimens (sputum, blood, FeNO) are collected again at 4 and 8 weeks. Control subjects undergo the same measurements, but do not receive any intervention.

Schedule of Events

	Asthma (A) or Control (C)	Visit 1/Week 0 (Screening) (+/- 3 days)	Visit 2/Week 4 (+/- 3 days)	Week 6 (+/- 3 days)	Visit 3/Week 8 (+/- 3 days)	Week 10 (+/- 3 days)	Visit 4/Week 12 (+/- 3 days)	Week 14 (+/- 3 days)
Informed Consent	A,C	X						
Site Visit	A,C	X	X		X		X	
Phone Call	A			X		X		X
Confirmation of Eligibility	A,C	X	X					
Randomization	A		X					
Drug Dispensation	A	X ^{1,2}	X ^{1,2,3}		X ^{1,2,3}		X ^{1,2}	
Demographics	A,C	X						
Medical History Review	A,C	X						
Asthma History	A	X						
Smoking History	A,C	X						
Concomitant Medication Review	A,C	X	X		X		X	
Physical Exam/Vital Signs	A,C	X	X		X		X	
Asthma Control Test	A	X						
Demographics Questionnaire	A,C	X						
Family History Questionnaire	A,C	X						
Work Exposures Questionnaire	A,C	X						
Home Exposures Questionnaire	A,C	X						
Physical Activity Questionnaire	A,C	X						
Secondhand Smoke Exposure Questionnaire	A,C	X						
Peak Flow Meter Readings ⁵	A	X	X	X	X	X	X	X
Electronic Diary ⁴	A	X	X	X	X	X	X	X
ECG	A,C	X	X		X		X	
Spirometry with Reversibility ⁶	A,C	X	X		X		X	
Exhaled NO	A,C	X	X		X		X	
Urine Pregnancy Test ⁷	A,C	X						
Methacholine Challenge ⁸	A,C	X	X		X		X	
Sputum Induction	A,C	X	X		X		X	
Oral Wash	A,C	X	X		X		X	
Complete Blood Count with Platelet Count and Differential Blood Sample	A,C	X			X			
Serum IgE Blood Sample	A,C	X						
RAST Blood Analysis	A,C	X						
Research Blood Samples	A,C	X			X			
Adverse Events Review	A,C		X	X	X	X	X	X
Compliance/Adherence to Diary and Study Drugs	A	X	X	X	X	X	X	X

1. Dispensation of albuterol to asthmatic subjects (if required at Visit 2 and Visit 3)
2. Dispensation of ICS/LABA to asthmatic subjects
3. Dispensation of azithromycin/placebo to asthmatic subjects

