4. Diary is completed twice daily by asthmatic subjects at home. Compliance will be reviewed at every visit (clinic or telephone).
5. Peak flow meter readings are done twice daily. Compliance will be reviewed at every visit (clinic or telephone).
6. Reversibility only conducted on those subjects with an $FEV1\% < 60\%$ predicted.
7. Only required for females of child-bearing potential
8. Methacholine challenge only conducted on subjects whose $FEV1\% > 60\%$ predicted.

Inclusion criteria (All participants):

1. Age 18 - 55 years
2. Able to provide informed consent
3. QTc < 440 ms on ECG
4. Smoking history < 10 pack-years

For subjects with poorly controlled asthma

1. Methacholine PC20 ≤ 16 mg/ml
2. Albuterol response $\geq 12\%$ on FEV1 after 4 puffs of albuterol
3. Ability to use combination ICS + LABA
4. Meet definition for Th2-low asthma: peripheral blood eosinophil count < 300 and exhaled nitric oxide level < 30 ppb.

Exclusion criteria:

1. History of allergy or intolerance to any medications used in this study
2. Medication exclusions:
 - a. Current use of medications that prolong QTc interval
 - b. Current use of omalizumab or other anti-IgE therapies
 - c. Current use of anti IL 5 therapies
 - d. Current use of anticoagulants
 - e. Prednisone or other oral steroids within past 3 months
3. Pregnancy or lactation
4. Other respiratory or inflammatory disorders (e.g., sarcoidosis, emphysema)
5. Pre-existing liver disease (AST or ALT $> 10\%$ above the upper limit of normal)
6. Smoking within the last 6 months
7. Exacerbation of asthma in past 3 months
8. Affected by a hearing disorder
9. Clinically significant medical condition (e.g., heart failure, seizure disorder) which may increase risk as determined by study investigator
10. Corrected QT interval > 450 msec. Patients with known cardiac history or prolonged QT interval on a screening EKG are excluded given the small but real potential for macrolide-related side effects (49-54).

Recruitment

Subjects will be recruited from the Pulmonary and General Medicine clinics at the University of Chicago and at Northwestern University. We will also use advertisements including online, flyer and posters.

Duration of protocol

Participation may be up to 14 weeks.

Location where research is to be conducted

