Long-acting beta agonist therapy (salmeterol): Common: headache, dizziness, lightheadedness, insomnia, nausea, dry mouth and throat irritation.

Short-acting beta agonist therapy (albuterol): Common: nervousness, shaking of a part of the body, headache, irritation of the throat, cough, and muscle, bone or back pain.

Pregnancy

Women of childbearing potential will undergo a pregnancy test on the day of study entry and at each visit. They must have a negative urine pregnancy test to be eligible for study entry. If the

test is positive, the study physician will discuss the matter with the participant. If a participant becomes pregnant before completing the study, they will be asked to notify one of the study doctors immediately. The investigator shall counsel the subject and discuss the risks of continuing with the pregnancy and the possible effects on the fetus. Monitoring of the pregnant subject shall continue until the conclusion of the pregnancy. Pregnancies will be reported to the data and safety monitoring board (DSMB) within one day of the site's awareness. Should the pregnancy result in a congenital abnormality or birth defect, a SAE will be submitted to the IRB, DSMB and NHLBI using the SAE reporting procedures described below.

Confidentiality

Each subject will be assigned a sequential identification number. This number will be linked to the subjects name and data.

We maintain strict confidentiality of all data to minimize the risk of inappropriate access or dissemination of such information. All protected health information including genotype data is saved on a password-protected computer or CRI server in a locked office with limited access. Only staff listed on this protocol will have access to the subjects name and data.

Data sent outside the University of Chicago or Northwestern University, will be sent using an identification number and not the participant's name.

Outcome Measures

Primary:

- ✓ ACT score change from 0 (baseline) to 8 weeks

Secondary:

- ✓ Change in FEV1 from 0 (baseline) to 8 weeks
- ✓ Sputum eosinophils change from 0 (baseline) to 8 weeks
- ✓ Sputum neutrophils change from 0 (baseline) to 8 weeks
- ✓ COMPEX score of asthma severity (from daily diary)
- ✓ Microbiome Shannon alpha-diversity score change from 0 (baseline) to 8 weeks
- ✓ Microbiome beta-diversity score change from 0 (baseline) to 8 weeks
- ✓ Microbiome change in relative proportion of top 10 genera from 0 (baseline) to 8 weeks

Data management

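### The primary ACT outcome is scheduled inconsistently, and neither its baseline nor its 8-week visit is named, so three visit pairs are possible

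*Combined protocol and SAP*

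**What the plan says.** - **Outcome Measures, primary:** "ACT score change from 0 (baseline) to 8 weeks". The first paragraph of Statistical analysis compares mean within-subject change over the same span by two-sample t-test. Neither place gives a visit number or defines baseline.
- **Schedule of Events:** the "Asthma Control Test" row carries one mark, at Visit 1/Week 0, the screening visit. Randomization is marked in the column headed "Visit 2/Week 4 (+/- 3 days)". Visit 3 is labelled Week 8 and Visit 4 Week 12.
- **Study Design:** "This pilot protocol examines the change in the airway microbiome after azithromycin over an 8 week period". After the first round of measurements, "Participants with asthma then are randomized 1:1 to receive azithromycin, 250 mg, or placebo, daily for 8 weeks". Then: "Clinical parameters including ACT, oral wash, adherence, side-effect profile, spirometry, and biological specimens (sputum, blood, FeNO) are collected again at 4 and 8 weeks". This paragraph does not mention a run-in.
- **Study Drug:** a four-week run-in separates Visit 1 from Visit 2, and study drug is taken for 8 weeks from Visit 2 to the end of Visit 4.
- **Asthma medications during the study:** the study ICS/LABA inhaler starts on the day of Visit 1 and may differ from what the subject used before.
- **Statistical analysis, CompEx:** time to event is counted from a baseline with no stated day, and a diary event is a change from a baseline whose diary days are not stated in the protocol.

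**The concern.** There are two separate faults. First, the Schedule and the Study Design text disagree on whether the ACT is repeated at all, and the ACT is the primary outcome. Second, even with the ACT row corrected, the phrase defining the outcome can be read on two clocks: the Schedule's week labels, which start at screening, or weeks on study drug, which start at Visit 2.

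If the window is left open, the primary endpoint may not be collected, or it may be taken at mid-treatment. If baseline is Visit 1, the change score also contains whatever happened during run-in, including any response to the newly started controller. The choice of visits could then also be made after the data are seen. The same unnamed baseline applies to the secondary change outcomes and to the CompEx clock.

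**Working it through.** **1. The plan's own figure.** The documents give no power or precision figure for the ACT. The only calculation, under Power calculations, is for *Pseudomonas* abundance before and after azithromycin in 20 patients. It reproduces if the 1.8 is taken as an SD:

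- SD of change = 1.8 × √(2(1 − ρ)) = 1.394 at ρ = 0.7 and 1.800 at ρ = 0.5.
- Detectable change at 80% power (paired t, 19 df) = 0.92 and 1.19, against the stated 0.9 and 1.2.
- 95% half-width = t × SD/√20 = 0.65 and 0.84, against the stated 0.7 and 0.84.

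This has no bearing on the ACT window, except that it shows a single-arm before-and-after estimate is planned.

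**2. Days in each window.** Inputs from the Schedule and the Study Drug section: Visit 1 = day 0; Visits 2, 3 and 4 nominally on days 28, 56 and 84; ±3 days gives 25–31, 53–59 and 81–87. Study drug runs from Visit 2 to Visit 4.

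| Reading | Run-in days | Drug days | Share of the nominal 56 drug days | ACT marks in the Schedule |
|---|---|---|---|---|
| Visit 1 to 3 | 28 (25–31) | 56 − 28 = 28 (53 − 31 = 22 to 59 − 25 = 34) | 28/56 = 50% | baseline only |
| Visit 2 to 4 | 0 | 84 − 28 = 56 (81 − 31 = 50 to 87 − 25 = 62) | 56/56 = 100% | neither |
| Visit 1 to 4 | 28 (25–31) | 56 (50–62) | 56/56 = 100% | baseline only |

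With one mark in four site visits, none of the three change scores can be formed from the Schedule.

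**3. What supports each reading.**

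- *Visit 1 to 3* matches the labels Week 0 and Week 8 exactly. It ends mid-treatment and leaves out the Visit 4 spirometry, FeNO, sputum and oral wash.
- *Visit 2 to 4* is the only interval that is both 8 weeks long and the full treatment period. It fits the Study Drug section and the pre- to post-azithromycin comparison under Microbial bioinformatics. The Schedule does not mark an ACT at Visit 2.
- *Visit 1 to 4* takes the one ACT the Schedule marks before study drug and counts 8 weeks from randomization, as the order of the Study Design sentences suggests. It spans 12 weeks in all.

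**4. Effect on the estimates.** Write the change from Visit 1 as R + D, where R is the run-in change and D the change after randomization.

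- *Between arms:* R is complete before allocation, so its expected value is the same in both arms and cancels. The contrast is unbiased on all three readings.
- *Within one arm:* the expected change is E(R) + E(D). A before-and-after estimate from Visit 1 counts any run-in response to the controller as change with azithromycin.
- *Precision:* for equal SDs at each visit, the variance of change is 2σ²(1 − ρ). A Visit 1 baseline adds noise if Visit 1 correlates less with the endpoint than Visit 2 does. The documents give neither correlation, nor any ACT SD or effect, so no power loss is calculated.

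**5. Other outcomes.** Spirometry and sputum induction are marked at all four site visits, so no data are lost for those change outcomes; only the visit pair is open. If the CompEx clock started at Week 0, events before randomization would be counted, although they cannot reflect treatment.

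**The case against.** **The intent is clear from context.** The Study Design sentence on repeat measurements follows the randomization sentence, that paragraph has no run-in, and the drug period ends at Visit 4. This stands in part: the text does lean towards counting 8 weeks from randomization, and Visit 1 to 3 is the weaker reading. It settles the end of the window better than the beginning, because it does not say whether the pre-drug ACT is the one at Visit 1 or one at Visit 2. The zero in the outcome wording matches the Schedule's Week 0.

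**The single mark is clerical, or marks were lost in the copy.** Clerical omission is plausible, and sites may well follow the text. Loss in copying is less likely: the row keeps its full set of cells, and neighbouring rows such as ECG, spirometry and FeNO keep four marks. Even if marks were lost, the unnamed window remains, because it rests on running text and column labels.

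**CompEx may be settled elsewhere.** The event definition is taken from a cited publication, which may fix the diary baseline. Comparing two arms also implies a start at Visit 2. Both points are fair; the protocol still should state day zero.

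**A reader might infer more than the documents support:**

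- *That sizing of the future trial depends on this window.* Purpose, objective b, does collect the microbiome response "so that we can generate appropriate power calculations and sample size estimates for the future RCT". However, the Poisson modeling paragraph bases that sizing on fitted Poisson and multivariate models, with treatment and time effects tested at each time point, not on one change score.
- *That the primary outcome covers only half of treatment.* That is true of one reading in three.
- *That a known share of CompEx follow-up precedes randomization.* No text starts that clock at Week 0.

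**Conclusion.** The point holds. The Schedule and the Study Design text contradict each other on the primary outcome, and no section fixes its baseline and endpoint visits. Followed as written, the Schedule supports none of the three possible windows. These hold 28, 56 or 56 nominal drug days, with 28, 0 or 28 run-in days.

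The consequence is conditional. The endpoint goes uncollected only if sites follow the Schedule over the text, and drug exposure is halved only on the Visit 1 to 3 reading. It would be wrong to infer a biased comparison of arms, since randomization protects it on every reading. The day counts assume visits timed from Visit 1 and study drug taken from Visit 2 to Visit 4. Because this is the primary outcome and the repair is cheap, it should be corrected before any outcome data are examined.

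**What to change.** 1. **Schedule of Events:** mark the ACT at Visits 2, 3 and 4 as well as Visit 1. Name the same visits in the Study Design sentence on repeat measurements.
2. **Outcome Measures and Statistical analysis:** define baseline as Visit 2 (randomization) and the endpoint as Visit 4 (8 weeks after randomization) for the ACT and the other change outcomes. Keep Visit 1 as a descriptive pre-run-in value. Naming the visits is the minimum. Visit 2 to Visit 4 is preferred because it covers exactly the period on study drug.
3. **CompEx:** start the clock at randomization and state which run-in diary days form the baseline. The data exist, since "Diary is completed twice daily by asthmatic subjects at home" and the diary row is marked from Visit 1.

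**Cost:** wording edits and three marks at visits that already occur. For 40 asthma subjects the proposal needs 4 × 40 = 160 ACTs. Against the Schedule (1 × 40 = 40) that adds 120, or three per subject. Against the Study Design text (3 × 40 = 120) it adds 40, or one per subject. No new visit or diary collection is needed.

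The Study Design text also lists blood among the specimens repeated at 4 and 8 weeks, whereas the repeat blood samples are marked in the Schedule only at Week 8. That is a separate item for the sponsor to reconcile.

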For demographic and clinical data we use a HIPAA compliant, web-based REDCap data management system residing on a password-protected network. REDCap is a web based, metadata-driven software application developed at Vanderbilt University (Harris et al, 2009) that is maintained by the Center for Research Informatics (CRI) at the University of Chicago. Northwestern University uses the same REDCap system. It allows for range and consistency checks during initial data entry to detect errors, and has built-in features for exporting data into Excel, SAS, STATA, or R files. Files exported from REDCap will be linked to the microbiome data using a unique patient ID number. Double-entry systems will be used to minimize coding error: our experience with our U19 AACRC and with AsthmaNet has found that such double-entry reduces significantly the error-rate in getting information into accessible web forms, and retention

of the paper CRFs ensures proper audit procedures. For biospecimen tracking, we use a web based application with a MYSQL database and a robust security model.

Data and Safety Monitoring Board (DSMB)

The Board will consist of three members at the University of Chicago and at Northwestern University who are not part of this study. Members are [name], [name] (Chair), and [name] (biostatistician). The DSMB will meet every 6 months to review all safety data and make recommendations to the NHLBI regarding continuation of the trial. A copy of the Data Safety and Monitoring Plan (DSMP) is located in Appendix 1.

Statistical analysis

Effect of treatment on clinical outcomes. Descriptive statistics will be generated to summarize the demographic and clinical characteristics of the asthma patients at baseline stratified by treatment arm. To compare changes in clinical parameters of interest, we will perform two-sample t-tests comparing the mean within-subject changes from baseline to 8 weeks. The primary and secondary outcomes measures are listed above.

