For the COMPEX scores, we will determine the time to deterioration as defined in Fuhlbrigge et al (2017). This criteria defines a “diary event” as reaching a predefined change from baseline (threshold) for at least 2 consecutive days, or deterioration in all six variables comprising the COMPEX score over at least a 5-day period plus at least one variable reaching a threshold criterion for at least 2 consecutive days. A “CompEx event” is then defined as the first occurrence of either a diary event or a severe asthma exacerbation (deterioration of asthma leading to oral corticosteroid use, emergency room admission, or hospital admission). Patients who do not experience a CompEx event will be censored as of the last negative assessment. The time from baseline to a CompEx event in days will be compared in the two treatment arms using a logrank test.

Data analysis will be performed using R and STATA software. Linear mixed effects models will be fit for continuous longitudinal outcomes and ordinal, logit, and Poisson mixed effects models will be employed for ordinal, binary, and count responses, respectively (59).

Initial microbiome analysis. Microbiome analysis is done in collaboration with [name], who is Director of The Microbiome Center at the University of Chicago, which houses an advanced sample processing and sequencing core. Samples are partitioned into two aliquots: one for PCR amplification and analysis of the 16S rRNA V4-V5 hypervariable region using amplicon sequencing. We will independently do qPCR of total 16S rRNA of each sputum, oral and nasal sample to determine total load. We will use the Illumina MiSeq platform and barcoded primers to sequence PCR-libraries, and always include non-template and blank controls. The remarkable simplicity of airway microbiota allows a high level of multiplexing (>300 samples per MiSeq flow cell) and ensures 99.99% sequencing coverage after 10,000 reads.

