
We will analyze changes from the pre- to post-azithromycin treatment, and between azithromycin and placebo subjects, in 1) abundance of key microbial genera (e.g., *Pseudomonas*, on which our first power calculations are generated, as well as *Streptococcus* and *Hemophilus*), 2) change in alpha-diversity, richness and evenness indices, 3) principal coordinate analysis (PCoA) and non-metric multi-dimensional scaling (NMDS) of beta-diversity indices, and 4) com-

parisons of key changes to clinical parameters of most compelling interest: ACT score, methacholine responsiveness, FEV1, markers of airway inflammation such as BAL eosinophils and neutrophils, BAL concentrations (measured by multiplex assay) of Th2 related cytokines such as IL-5 and IL-13, IL-17 related cytokines such as IL-17a, and TGF- β 1. The measurement of Th17-related cytokines is particularly important as we anticipate that 70% of our subjects will have a blood eosinophil count < 300 per μ l or BAL eosinophil proportion < 3%, and azithromycin may be more effective in patients with eosinophil-low asthma (20).

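### Sputum eosinophil change is tested without baseline adjustment on an unspecified scale: valid, but inefficient if the values are skewed, as is likely

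*Combined protocol and SAP*

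**What the plan says.** In the combined protocol and SAP, Outcome Measures lists "Sputum eosinophils change from 0 (baseline) to 8 weeks" among seven secondary outcomes. It does not say whether this is a percentage or an absolute count.

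Statistical analysis, under effect of treatment on clinical outcomes, states: "we will perform two-sample t-tests comparing the mean within-subject changes from baseline to 8 weeks". It then points to the listed primary and secondary outcomes. No transformation, rank test, baseline covariate or rule for zeros is given.

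The same section adds "Linear mixed effects models will be fit for continuous longitudinal outcomes", and says that "ordinal, logit, and Poisson mixed effects models will be employed for ordinal, binary, and count responses, respectively". None of these models is assigned to sputum eosinophils.

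On who is enrolled, the asthma inclusion criteria say: "Meet definition for Th2-low asthma: peripheral blood eosinophil count < 300 and exhaled nitric oxide level < 30 ppb". There is no sputum criterion. Microbial bioinformatics says "we anticipate that 70% of our subjects will have a blood eosinophil count < 300 per" microlitre or "BAL eosinophil proportion < 3" percent. That 3% refers to lavage fluid, not sputum. The 70% has to be reconciled with an entry rule that would make the blood-count share 100%.

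**The concern.** Sputum eosinophils cannot fall below zero and are likely to be right-skewed. On the raw scale, a few patients with high values supply much of the variance of the change. A proportional effect is then harder to detect than on the log scale.

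Subtracting the baseline also costs precision whenever the pre/post correlation is below 1, because the change score carries the noise of both measurements. A model with baseline as covariate uses only as much of the baseline as is informative.

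The pilot exists to supply planning data for a full-scale trial. At stake is a less precise treatment estimate and a variance that a few patients may dominate. False positives are not the issue.

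**Working it through.** **The plan's own figure.** No power statement exists for sputum eosinophils. The only one concerns *Pseudomonas* abundance, with SD 1.8 and 20 evaluable patients in a paired comparison. The SD of change is 1.8 x sqrt(2(1 - rho)), which is 1.39 at rho = 0.7 and 1.80 at rho = 0.5. A paired t-test with 80% power then detects 0.92 and 1.19, against the stated 0.9 and 1.2. The 95% CI half-widths are 0.65 and 0.84, against the stated 0.7 and 0.84. The figure reproduces but does not bear on eosinophils.

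**Inputs.**
- From the documents: 40 asthma patients randomized 1:1, so 20 per arm. Two-sided 0.05 and rho = 0.5 are borrowed from the *Pseudomonas* statement.
- Assumed: the outcome is a percentage; values are log-normal with median 0.5, 1 or 2% and log-SD 0.5, 0.8 or 1.1; 400 cells are counted, with binomial error; the effect is a halving at week 8; nobody drops out.

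**Analyses compared.** Let X be the baseline and Y the week-8 percentage.
1. Planned: t-test on Y - X.
2. Log change: t-test on log(Y + 0.25) - log(X + 0.25).
3. Raw adjusted: Y on arm and X.
4. Log adjusted: log(Y + 0.25) on arm and log(X + 0.25).

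**Why adjustment helps.** With equal variances, a change score has variance 2s²(1 - rho) and the adjusted analysis s²(1 - rho²). The ratio adjusted/change is (1 + rho)/2, or 0.75 at rho = 0.5 and 0.85 at rho = 0.7. Counting error lowers the observed correlation below the underlying 0.5, which favours adjustment further.

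**Power (%) for a halving**, 4,000 simulated trials per setting. Each cell shows baseline uncapped / baseline capped at 3%.

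| Median | Log-SD | Planned | Log change | Raw adjusted | Log adjusted |
|---|---|---|---|---|---|
| 0.5 | 0.5 | 34 / 34 | 38 / 37 | 61 / 61 | 59 / 59 |
| 0.5 | 0.8 | 25 / 27 | 30 / 32 | 45 / 44 | 47 / 47 |
| 0.5 | 1.1 | 17 / 22 | 25 / 26 | 28 / 28 | 36 / 36 |
| 1 | 0.5 | 48 / 51 | 57 / 57 | 77 / 79 | 76 / 78 |
| 1 | 0.8 | 33 / 40 | 44 / 43 | 56 / 55 | 60 / 59 |
| 1 | 1.1 | 19 / 28 | 32 / 33 | 32 / 33 | 44 / 42 |
| 2 | 0.5 | 64 / 74 | 77 / 77 | 91 / 90 | 91 / 90 |
| 2 | 0.8 | 37 / 54 | 56 / 56 | 62 / 63 | 71 / 67 |
| 2 | 1.1 | 18 / 33 | 35 / 38 | 32 / 35 | 48 / 45 |

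Uncapped, the extremes are 17-64% planned and 36-91% log adjusted. Capped, they are 22-74% and 36-90%. The slightly wider ranges quoted in the verdict (14-66% and 33-93%; 20-75% and 35-92%) allow for variation between simulation runs.

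**Where the gain comes from.** With the cap, moving from raw change to log change adds about 2-6 points, and adding the baseline covariate adds a further 8-22. At log-SD 0.5 the raw adjusted analysis does as well as the log adjusted one. At log-SD 1.1 the order of the two steps matters, because each helps the other.

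**Type I error** in the same settings was about 4-5% for the planned test and 4-6% for the log adjusted analysis.

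**Effect of the offset.** At the median, a true ratio of 0.50 becomes:
- 2% to 1%: 1.25/2.25 = 0.56
- 1% to 0.5%: 0.75/1.25 = 0.60
- 0.5% to 0.25%: 0.50/0.75 = 0.67

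The simulated estimates ran from 0.54 to 0.68.

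**The case against.** The strongest objection is that the distribution is assumed. The documents give no sputum mean, SD, skewness or share of zeros. A reader might infer that selecting low-eosinophil patients places sputum values near zero with a long upper tail, so that the raw scale alone forfeits most of the power and the outcome will probably be reported as unchanged. The documents do not support that. Entry is by blood count and exhaled nitric oxide, the 3% is a lavage figure, and only 70% are expected to be eosinophil-low. Selection may also cut the upper tail: with a 3% baseline cap, the log scale alone gains only a few points. A log-change t-test would itself often miss a halving (25-77% power in the table). This part of the objection stands, so no claim is made about the true distribution or the likely result.

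Second, no passage predicts a proportional effect of azithromycin on sputum eosinophils; the hypothesised responders are neutrophil-dominant. That also stands, and the halving is only a yardstick.

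Third, the plan does not use the word raw, and it mentions mixed models. A linear mixed model with a common baseline mean could recover much of the adjustment gain. But no model is assigned to this outcome, while the t-test is tied to the listed outcomes, and a model of untransformed values would keep the scale problem.

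Fourth, this is one secondary outcome in a self-described exploratory protocol with no power claim for it, and a log analysis changes the target to a ratio. True, and it limits the weight of the point. It does not remove the gain, which appeared in every setting tried.

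**Conclusion.** The point holds as an inefficiency, not an error. The planned unadjusted t-test controls type I error but makes poor use of the baseline and handles skew badly. Under the assumed log-normal inputs, power for a halving is about 14-66% as planned and 33-93% with the log value adjusted for baseline. With baseline capped at 3%, it is about 20-75% and 35-92%, with most of the gain from adjustment rather than the log scale.

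These ranges depend on the assumed median, spread, cell count, proportional effect and correlation of 0.5. A higher correlation would shrink the adjustment gain. A reader might take the figures as the power this trial will have, but the documents give no data from which to know that. The importance is low: one secondary outcome in an exploratory pilot.

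**What to change.** State in the SAP, before unblinding, that sputum eosinophils are analysed as a percentage. The model is week-8 log(percent + 0.25) on arm, with baseline log(percent + 0.25) as covariate. Report the arm effect with 95% CI as a ratio of geometric means of (percent + 0.25), and say that the offset pulls it toward 1. Repeat the analysis with another offset as a sensitivity analysis. Keep the raw mean change in each arm, with 95% CI, as a descriptive figure. Say that this replaces the t-test for this outcome.

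The cost is a few sentences of SAP text; no visits, samples or measurements are added. The downside is that the effect becomes a ratio instead of a percentage-point difference and depends somewhat on the offset.
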